3 RESEARCH DESIGN

3.1 Study Methodology

Observational, Prospective, Multicenter Study

3.2 Conduct of the Study

The Study is conducted according to the usual management schedule for these patients.

After inclusion of the patient, there will be postoperative follow-up or in the months following the procedure and at 6 months, 12 months and annually, for 5 years.

The clinical and radiological follow-up will be performed according to the follow-up protocol recommended by HAS and by Learned Societies (Société de Chirurgie Vasculaire [Society for Vascular Surgery] – Société Française de Radiologie [French Society of Radiology])¹.

	Post-operative follow-up (D1 to D30)	Follow-up at 6 months.	Follow-up at 1, 2, 3, 4 and 5 years	Follow-up intermediate ***
Clinical examination	X	X	X	X
Radiography of the abdomen without preparation in 3 effects (front, profile and ¾)	X ¹	X*	X*	X*
CT with contrast medium	X	X	X	X
MRI	X*	X*	X*	X*
Vascular Doppler	X**	X**	X**	X**

* if CT with contrast medium cannot be performed

** if MRI cannot be performed

*** interim follow-up carried out only in case of leakage, deterioration of the endoprosthesis or scalability of the aneurysm on the previous control examination. Follow-up to be carried out 3 months after the control where the anomaly was observed.

¹ Radiography in postoperative follow-up will not be necessary in case of 3D reconstruction performed during the CT.

An annual report will be forwarded to CNEDiMTS.

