1.1.3 Requirements of the French National Authority for Health

The opinion of the National Commission for the Evaluation of Medical Devices and Health Technologies (CNEDiMTS) of July 13, 2010 (Appendix 1) indicates that:

Terms of renewal:

CNEDiMTS subjects the renewal of registration of each endoprosthesis to the presentation of results of a specific follow-up study implemented on a cohort of patients representative of the population treated in real life conditions.

The objective of each study is to evaluate the usefulness of the technique by documenting overall mortality, complications (endoleak, migration), the rate of surgical conversion, evolution and rupture of the aneurysm, in the long term, that is, beyond 5 years.

This prospective cohort study shall involve at least 150 patients implanted after registration on the LPPR [List of Reimbursable Products and Services].

The results of the follow-up study shall be forwarded to CNEDiMTS once a year, for consideration.

The follow-up evaluation may lead CNEDiMTS to recommend that reimbursement for the abdominal aortic endoprosthesis concerned be maintained or suppressed.

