3.3 Evaluation Criteria

These criteria are measured postoperatively or within one month after surgery, at 6 months, 12 months and then annually for 5 years, with an annual report issued to be submitted to the French National Authority for Health:

- Overall mortality rate,
- Mortality rate related to the aneurysm,
- Evolution of the diameter of the aneurysm
- Rate of Endoleaks for Type I, II and III
- Migration rate,
- Rate of surgical conversion,
- Rate of endovascular or surgical re-intervention.

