3.4 Evaluation Parameters

General Data

- Age
- Gender
- Diameter of Abdominal Aortic Aneurysm
- Patient status (normal or high surgical risk according to the Afssaps criteria, Appendices 3 and 4)
- All references and evolution of the range of the GORE® EXCLUDER Endoprosthesis®

Data related to the procedure (at all control times):

- Death from all causes
- Aneurysm-related death
- Evolution of the diameter of the aneurysm
- Types I, II and III endoleak
- Migration
- Surgical conversion
- Re-intervention related to the initial procedure

Definitions :

Death related to the aneurysm shall be defined as any death occurring as a result of a ruptured Abdominal Aortic Aneurysm or following any procedure intended to treat Abdominal Aortic Aneurysm.

If the death occurred within 30 days of any procedure intended to treat Abdominal Aortic Aneurysm, then it will be considered as related to the aneurysm unless proven otherwise. Deaths occurring beyond 30 days of any procedure intended to treat Abdominal Aortic Aneurysm and that are related to the procedure should be considered as related to the aneurysm.

Distal migration is defined by a distal displacement strictly greater than 10 mm. Proximal migration is defined either by proximal displacement strictly greater than 10 mm, or by proximal displacement which covers one of the renal arteries; the reference examination being the first postoperative CT performed.

An increased aneurysm diameter is defined as an increase strictly greater than 5 mm of the largest measurable diameter of the aneurysm; the reference diameter being the diameter of the first post-operative check-up.

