6.2.2 Criteria Studied

Main analyses:

The criteria studied are as follows:

- Death from all causes
- Aneurysm-related death
- Evolution of the diameter of the aneurysm.
- Types I, II and III endoleaks
- Migration
- Surgical conversion
- Re-intervention related to the initial procedure

Definitions :

- Death related to the aneurysm shall be defined as any death occurring as a result of a ruptured Abdominal Aortic Aneurysm or following any procedure intended to treat Abdominal Aortic Aneurysm.
If the death occurred within 30 days of any procedure intended to treat Abdominal Aortic Aneurysm, then it will be considered as related to the aneurysm unless proven otherwise. Deaths occurring beyond 30 days of any procedure intended to treat Abdominal Aortic Aneurysm and that are related to the procedure should be considered as related to the aneurysm.
- Distal migration is defined by a distal displacement strictly greater than 10mm. Proximal migration is defined either by proximal displacement strictly greater than 10mm, or by proximal displacement which covers one of the renal arteries; the reference examination being the first postoperative CT performed.

- An increase in the diameter of the aneurysm is defined by an increase strictly greater than 5 mm of maximum diameter of the highest measurable diameter of the aneurysm; the reference diameter being the diameter of the first post-operative check-up.

Each of the rates that match the Study criteria will be analyzed by calculating frequency distributions and bilateral confidence intervals of 95% (IC95) associated.

Event rates over time are described by survival curve according to the Kaplan-Meier method and the related Kaplan-Meier estimators will be calculated.

Additional Analyses:

All the analyzes may be stratified by center if recruitment in each center participating in the study is sufficient for such analyzes to be of interest. However, it must be emphasized that this Protocol in no way aims to compare the centers.

For exploratory purposes, the study criteria will also be analyzed depending on patient baseline characteristics:

- Age (in categories)
- Gender
- Diameter of Abdominal Aortic Aneurysm
- Patient status (normal or high surgical risk according to the Afssaps criteria, Appendices 3 and 4)

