6.4 Method of management of missing, unused or invalid data

Missing data will be listed and presented in a tabulated form.

Patients will be considered as censored at the date of the last observation.

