### 2.4.3.1. Primary Analysis

The 5-year mortality survival curve will be described according to the Kaplan-Meier method. The associated Kaplan-Meier estimators will be calculated. Only events occurring up to 5 years (1826 days) of follow-up will be analyzed for mortality survival curve.

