### Summary table

	Mod 1 (n=X)	...	Mod n* (n=X)
Nb of patients	X	...	X
Nb of patients with an event	X (XX.XX%)	...	X (XX.XX%)
Nb of patients without an event	X (XX.XX%)	...	X (XX.XX%)
Survival rate	XX %	...	XX %
Progression-Free survival (days)		...	
Median	XX	...	XX
(95% CI)	(XX, XX)	...	(XX, XX)
25th-75th percentile	XX.X – XX.x	...	XX.X – XX.x
Range	X - X	...	X - X

\* If any

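### With survivors censored at their last observation and no visible data cut-off for the annual reports, deaths recorded between controls inflate the tail of the interim mortality curve

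*Protocol*

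**What the plan says.** - **Reporting.** Protocol 1.1.3 relays the commission's requirement: "The results of the follow-up study shall be forwarded to CNEDiMTS once a year, for consideration". Protocol 3.2 repeats the commitment: "An annual report will be forwarded to CNEDiMTS". Protocol 3.3 puts overall mortality, aneurysm-related mortality and re-intervention among the criteria and gives the timing: "These criteria are measured postoperatively or within one month after surgery, at 6 months, 12 months and then annually for 5 years".
- **Collection.** Protocol 3.4 lists death under the heading "Data related to the procedure (at all control times"). It does not say how a death learned of between two controls is handled.
- **Estimator.** Protocol 6.2.2: "Event rates over time are described by survival curve according to the Kaplan-Meier method". SAP 2.4.3.1 makes the 5-year mortality curve the primary analysis.
- **Censoring.** Protocol 6.4: "Patients will be considered as censored at the date of the last observation". The term for the censoring date is not defined further.
- **Limit on events.** SAP 2.4.3.1: "Only events occurring up to 5 years (1826 days) of follow-up will be analyzed for mortality survival curve". This limit runs on each patient's own clock (5 × 365.25 = 1826.25 days). It is not a calendar cut-off for a report.
- **Event dates.** SAP 2.4.3.2 dates diameter increase, endoleak and migration at the first visit that reports them. Death and re-intervention have no such rule in the visible text.
- **Display.** The summary table for survival curves (SAP 4.3.3, Type 10) has a row "Survival rate" with no time attached, and a median. It has no row for the number at risk.
- **Vital status.** Protocol 4.5 provides for a search only after a missed visit and failed contacts, not for every patient when a report is prepared.

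**The concern.** Kaplan-Meier needs the length of follow-up to be unrelated to the outcome. Here it may not be. Take two patients who both attended the 12-month control and are at month 20 when the report is prepared. One is alive and is censored at month 12. The other died at month 16 and the centre has recorded it, so this patient stays at risk to month 16 and counts as an event. Whether follow-up extends past the last control then depends on having died. The risk set in that stretch consists largely of patients already known to be dead, and each death takes a large step out of the curve.

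This needs no missed visit and no loss to follow-up. It arises for patients in regular follow-up because annual controls are 12 months apart. Under Protocol 1.1.3 the commission may use the yearly results to recommend that reimbursement be kept or withdrawn. A reader who takes the untimed survival rate or the median from the end of an interim curve would see mortality overstated.

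**Working it through.** **Inputs from the documents.** 180 patients included over 12 months (Protocol 3.5). Controls within the first month, at 6 and 12 months, then yearly to 5 years (Protocol 3.2). Survivors censored at the last observation (Protocol 6.4). The plan states no expected mortality and no interim estimate, so there is no figure of its own to reproduce.

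**Assumptions.** Uniform entry; constant mortality of 6% per year, with other rates as sensitivity; nobody lost; last observation means last control. Let q be the share of deaths since the last control that are already in the database at the report. The documents give no value for q.

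**Step 1: by hand, month-24 report, visits exactly on schedule, q = 100%.**
- Everyone has had the 12-month control and nobody has yet had the 24-month one.
- Expected alive at 12 months: 180 × 0.94 = 169.2.
- Follow-up beyond month 12 is uniform on 0 to 12 months, so mean survival over that stretch is 0.06 / (−ln 0.94) = 0.06 / 0.0619 = 0.970.
- Expected deaths after month 12 and before the report: 169.2 × (1 − 0.970) ≈ 5.1.
- All other patients are censored at month 12, so the risk set just after month 12 is about 5 patients, all of whom die. The first death should lower the curve by about 1/169 (0.6%) of its height. It lowers it by about 1/5 (20%), and the curve reaches 100% mortality at the last death.
- With q = 10%, about 0.5 such deaths are expected. The chance of at least one is roughly 1 − exp(−0.51) ≈ 40%. The average excess at small q therefore mixes reports with no false rise and reports with a steep one.

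**Step 2: simulation, annual visits spread from 1 month early to 2 months late.** True values are 1 − 0.94^1.5 = 8.9% at 18 months and 1 − 0.94^2.5 = 14.3% at 30 months. Repeat runs differ by a point or two.

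| q | Month-24 report, at 18 months (true 8.9%) | Month-36 report, at 30 months (true 14.3%) |
|---|---|---|
| 10% | about 15% | about 19% |
| 25% | about 25% | about 30% |
| 50% | about 35% | about 37% |
| 100% | about 45% | about 49% |

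In the month-24 report about 2–4 of the 180 patients are at risk at 18 months. With q = 0 the 18-month figure is 9.1%, so there is no upward bias. With q = 50% it is 29% at 4% per year (true 5.9%) and 45% at 9% per year (true 13.2%).

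**Step 3: a second set-up.** 8% per year, visits within 30 days either side, deaths not known at once found one month after the next missed visit. At 18 months in the month-24 report (true 1 − 0.92^1.5 = 11.8%) the curve gives 18.5%, 30.3%, 40.3% and 50.9% for q = 10%, 25%, 50% and 100%. With q = 0 it goes flat at 8.4%.

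**Step 4: where the curve is sound.**
- At 12 months in the month-24 report (6% per year): 5.8–6.4% against 6.0%, with about 105 patients at risk.
- At 48 months in the month-60 report (8% per year, q = 100%): 28.5% against 28.4%. At 54 months in the same report: 62.1% against 31.3%.
- At 5 years, once all patients have passed 5 years (8% per year): 34.1–34.7% against 34.1%.
- The point where the curve departs depends on each patient's own last control. In a month-18 report, late entrants are still held at 6 months, so at 8% per year and q = 100% the 12-month figure is already 10.0–10.5% against 8.0%.

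**Step 5: with deaths and follow-up both ended at the last control due.** At 6% per year: 6.0–6.1% against 6.0% at 12 months, and 11.6–11.7% against 11.6% at 24 months.

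**The case against.** - **Nothing says that deaths are counted up to the report date.** This stands. Protocol 3.3 and 3.4 tie the criteria to the controls. If deaths enter only through the next control, q is 0 and the false rise disappears. But no visible rule limits deaths in this way, and a share of 10% known early is already enough to matter.
- **The section where such a rule would sit cannot be read.** This stands. SAP 2.1.3 (Handling Missing Data) is in the table of contents but not in the text supplied, and the text after SAP 2.4.3.2 is redacted. A cut-off rule may exist, so the request is to confirm or add one.
- **Last observation need not mean last control.** This stands in part. A dated contact could count, and intermediate controls add observations for patients with an anomaly; the simulation leaves both out. Patients in uneventful routine follow-up have no scheduled contact between annual controls.
- **The large figures lie where almost nobody is followed.** This stands. A careful reader would quote the curve at controls reached, where it is nearly right. But the Type 10 summary table does not tie the survival rate to a time and shows no number at risk, so nothing in it warns the reader.
- **A reader might infer that every report, or the 5-year result itself, overstates mortality.** The documents and the calculation do not support this. The SAP's primary analysis is 5-year mortality, and once all patients have passed 5 years the rule barely affects it.

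**Conclusion.** The point holds for the interim reports, in the tail of the curve beyond the last control that patients have reached. The visible censoring rule, with no data cut-off, lets any death recorded after a patient's last control and before the next one is due inflate that tail, even with complete follow-up. At an assumed 6% per year, the 18-month figure in the month-24 report runs from about 15% to about 45% as the known share goes from 10% to 100%, against a true 8.9%. With a known share of zero there is no upward bias.

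The size rests on three assumptions: the mortality rate, the share of deaths known early, and reading the last observation as the last control. The documents settle none of them. Aneurysm-related death and re-intervention would be exposed in the same way if reported between controls; this was not simulated. The commission recommends on reimbursement from these reports, so the interim figures matter. The weight is low to moderate because the final 5-year estimate is almost untouched.

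**What to change.** Unless SAP 2.1.3 already does so, add to SAP 2.1.3 or 2.4.3:

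1. A data cut-off date for each annual report.
2. For each patient, end both deaths and follow-up at the last scheduled control due by that date, meaning that its visit window has elapsed. Count deaths up to that point and censor survivors there. List later deaths separately. The visible text gives no window for the annual controls, so the rule must name one.
3. Quote Kaplan-Meier estimates only at controls reached, with the number at risk. Attach a time to the survival-rate row of the Type 10 table.

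An alternative to item 2 is to confirm vital status for every patient at the cut-off date and censor survivors on that date. In the 8% per year set-up this gives 11.7% at 18 months in the month-24 report, against a true 11.8%. It requires contact about every patient at each report.

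The main option costs about two sentences in the SAP and one derived date per patient per report, with no new visits. Its downside is that the most recent deaths enter the curve one report later, though they still appear in the listing.

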3.3 Evaluation Criteria

These criteria are measured postoperatively or within one month after surgery, at 6 months, 12 months and then annually for 5 years, with an annual report issued to be submitted to the French National Authority for Health:

- Overall mortality rate,
- Mortality rate related to the aneurysm,
- Evolution of the diameter of the aneurysm
- Rate of Endoleaks for Type I, II and III
- Migration rate,
- Rate of surgical conversion,
- Rate of endovascular or surgical re-intervention.

3.4 Evaluation Parameters

General Data

- Age
- Gender
- Diameter of Abdominal Aortic Aneurysm
- Patient status (normal or high surgical risk according to the Afssaps criteria, Appendices 3 and 4)
- All references and evolution of the range of the GORE® EXCLUDER Endoprosthesis®

Data related to the procedure (at all control times):

- Death from all causes
- Aneurysm-related death
- Evolution of the diameter of the aneurysm
- Types I, II and III endoleak
- Migration
- Surgical conversion
- Re-intervention related to the initial procedure

Definitions :

Death related to the aneurysm shall be defined as any death occurring as a result of a ruptured Abdominal Aortic Aneurysm or following any procedure intended to treat Abdominal Aortic Aneurysm.

If the death occurred within 30 days of any procedure intended to treat Abdominal Aortic Aneurysm, then it will be considered as related to the aneurysm unless proven otherwise. Deaths occurring beyond 30 days of any procedure intended to treat Abdominal Aortic Aneurysm and that are related to the procedure should be considered as related to the aneurysm.

Distal migration is defined by a distal displacement strictly greater than 10 mm. Proximal migration is defined either by proximal displacement strictly greater than 10 mm, or by proximal displacement which covers one of the renal arteries; the reference examination being the first postoperative CT performed.

An increased aneurysm diameter is defined as an increase strictly greater than 5 mm of the largest measurable diameter of the aneurysm; the reference diameter being the diameter of the first post-operative check-up.

3.5 Duration of the Study

Duration of the inclusion period:

Inclusion period of 180 patients: 12 months

Duration of participation of each patient:

The requirement of the French National Authority for Health is long-term patient follow-up, that is, 5 years.

Total duration of the Research:

In this context, there is no maximum follow-up duration for this Study (12 months inclusion period and a minimum of 5 years of follow up).

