2 OBJECTIVE OF THE STUDY

The objective of this Study is to evaluate the usefulness of the technique by documenting:

- Overall mortality,
- Complications (endoleak, migration),
- The surgical conversion rate,
- The evolution and rupture of the aneurysm,

in the long term, that is, 5 years, on a cohort of patients representative of the population treated in real life conditions.

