Appendix 1: Opinion of HAS dated July 13, 2010

HAUTE AUTORITÉ DE SANTÉ
NATIONAL COMMISSION FOR EVALUATION OF MEDICAL DEVICES
AND HEALTH TECHNOLOGIES
OPINION OF THE COMMISSION

July 13, 2010

Devices : Abdominal Aortic Endoprosthesis (Title III - Chapter 1 - Section 1 - Subsection 2 - paragraph 4 of the list of products and services mentioned in Article L. 165-1 of the Social Security Code)

Pursuant to:

- Decree No. 2004-1419 of 23 December 2004 on the management of products and services mentioned in Article L. 165-13 of the Social Security Code authorizing the Evaluation of Products and Services Commission (CEPP), on its own initiative or at the request of Ministers in charge of Social Security, to reevaluate the expected or actual services of the products or services listed as provided for in Article L. 165-1 (Article 13 of the Decree);
- self-referral to CEPP dated April 5, 2006 relating, in particular, to post-registration study objectives required within the framework of the renewal of registration of Abdominal Aortic Endoprostheses listed under brand name;
- the proposals of the mandated Working Group;

the National Commission for Evaluation of Medical Devices and Health Technologies recommends amending the conditions for renewal of registration of Abdominal Aortic Endoprostheses, listed under the brand name, in the following manner.

Terms of Renewal

CNEDiMETS subjects the renewal of registration of each endoprosthesis to the presentation of results of a specific follow-up study implemented on a cohort of patients representative of the population treated in real life conditions.

The objective of each study is to evaluate the usefulness of the technique by documenting overall mortality, complications (endoleak, migration), the rate of surgical conversion, evolution and rupture of the aneurysm, in the long term, that is, beyond 5 years.

This prospective cohort study shall involve at least 150 patients implanted after registration on the LPPR [List of Reimbursable Products and Services].

The results of the follow-up study shall be forwarded to CNEDiMETS once a year, for consideration.

The evaluation of this follow-up may lead CNEDiMETS to recommend that reimbursement for the EPA concerned be maintained or suppressed.

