### 1.2. Study Design

The study is a observational, prospective and multicentric register of the GORE® EXCLUDER® AAA Endoprosthesis used to treat infrarenal abdominal aortic aneurysms in which 180 patients are enrolled from 29 sites and followed during 5 years minimum.

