#### 1.3.2. Patient's Follow-up

8 visits are scheduled:

- Visit 1 : Baseline
- Visit 2 : Procedure
- Visit 3 : Discharge
- Visit 4 : Post operatory (or in the month following the surgery)
- Visit 5 : 6 months Follow-up
- Visit 6 : 1 year Follow-up
- Visit 7 : 2 years Follow-up
- Visit 8 : 3 years Follow-up
- Visit 9 : 4 years Follow-up
- Visit 10 : 5 years Follow-up

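### The protocol gives the authority's horizon as 5 years where the opinion it appends says past 5 years, and the SAP's 1826-day limit stops the covered survival curves there and may exclude 5-year visit findings

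*Protocol*

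**What the plan says.** **The authority's horizon.** Protocol 1.1.3 reports the opinion of July 2010 as asking for outcomes "in the long term, that is, beyond 5 years". Appendix 1 reproduces the opinion with the same horizon: "evolution and rupture of the aneurysm, in the long term, that is, beyond 5 years".

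**The protocol's restatement.** Protocol 3.5 attributes a different horizon to the authority: "The requirement of the French National Authority for Health is long-term patient follow-up, that is, 5 years". The Summary does the same in its introduction and under duration of participation. The objective (Summary, Protocol 2 and SAP 1.1) follows the opinion's wording closely but reads "in the long term, that is, 5 years, on a cohort of patients representative of the population treated in real life conditions".

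**Length of follow-up.** Protocol 3.5 adds that "there is no maximum follow-up duration for this Study (12 months inclusion period and a minimum of 5 years of follow up"; SAP 1.2 says "180 patients are enrolled from 29 sites and followed during 5 years minimum". The last scheduled contact is "Visit 10 : 5 years Follow-up" (SAP 1.3.2), and the schedule in Protocol 3.2 also ends at 5 years.

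**The analysis limit.** SAP 2.4.3.1 states: "Only events occurring up to 5 years (1826 days) of follow-up will be analyzed for mortality survival curve". SAP 2.4.3.2 repeats the 1826-day limit for secondary curves, directly after a sentence naming diameter evolution, endoleak and migration. Protocol 6.2.2 and 6.4 contain no such limit; 6.4 censors patients at their last observation.

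**Durations and dating.** SAP 2.1.2 computes a duration as the later date minus the earlier date plus 1. SAP 2.4.3 and 2.4.3.2 date diameter, endoleak and migration events by the imaging exam or by the visit at which they are first reported.

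**The concern.** The study exists to meet this authority's condition for renewing reimbursement, and the opinion says reimbursement may be maintained or withdrawn on the results. A protocol that attributes 5 years to the authority, while appending a text that asks for more, leaves the target horizon unsettled. The SAP then settles it at the shorter horizon for the curves under the limit, although follow-up is open-ended. Whatever is collected after 5 years has no visible place in those curves.

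A second problem lies inside the first 5 years. Endoleak, migration and diameter increase are dated when they are seen. A limit at exactly 5 years in days falls on top of the 5-year visit, so a finding from that visit can be excluded because the visit took place on the anniversary or shortly after it.

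**Working it through.** **1. Reproduce the plan's figure.** 5 × 365.25 = 1826.25, which rounds to 1826. The conversion is correct.

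**2. Compare the horizons.**

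| Place | Horizon |
|---|---|
| Protocol 1.1.3; Appendix 1 | past 5 years |
| Protocol Summary (introduction, duration of participation); 3.5 | 5 years, attributed to the authority |
| Protocol Summary (objective); 2; SAP 1.1 | 5 years, as the study objective |
| Protocol 3.5; SAP 1.2 | at least 5 years; Protocol 3.5 adds no maximum |
| SAP 2.4.3.1; 2.4.3.2 | events to day 1826 only |

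The first two rows cannot both describe the authority's request unless a later agreement exists. None is cited in the available text.

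**3. How much follow-up could lie past 5 years?** The documents give 180 patients and 12 months of inclusion. They give neither a closing date nor survival or loss figures, so the following are assumptions: uniform accrual, and closure when the last patient reaches 5 years. Extra follow-up then runs from 0 to 12 months, with a mean of 0.5 year.

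- Ceiling, with no death or loss: 180 × 0.5 = 90 patient-years, out of 180 × 5.5 = 990 (9.1%).
- With 5-year retention S (alive and still followed) and a constant exit hazard h = −ln(S)/5: person-time to year 5 is 180 × (1 − S)/h. Person-time after year 5 is 180 times the mean of S(1 − e^(−hu))/h over u uniform on 0 to 1 year.

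| Assumed S | At risk at 5 years | Patient-years to 5 | Patient-years after 5 | Share after 5 | Exits after 5 |
|---|---|---|---|---|---|
| 0.8 | 144 | 806.7 | 70.9 | 8.1% | 3.2 |
| 0.7 | 126 | 757.0 | 61.5 | 7.5% | 4.4 |
| 0.6 | 108 | 704.7 | 52.2 | 6.9% | 5.3 |
| 0.5 | 90 | 649.2 | 43.0 | 6.2% | 6.0 |

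Exits are deaths and losses together. The curves under the limit would use none of the person-time after year 5. The first 5 years, about 91% to 94% of the total, stay in the analysis.

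**4. Where does the fifth anniversary fall?** Five calendar years here contain 1 or 2 leap days: 1825 + 1 = 1826 or 1825 + 2 = 1827 days. Under the SAP's rule, add 1: day 1827 or 1828. For assumed procedure dates from 1 March 2012 to 30 November 2015, 1,095 of 1,370 dates give 1827 and 275 give 1828. If the rule applies to event times, every finding first made on or after the anniversary is past day 1826. Without the added day, the anniversary is day 1826 or 1827, so a visit one day late is still past the limit. For death, dated when it occurs, this boundary effect is a day or two. For imaging findings it can remove the whole yield of a 5-year visit. The available text defines no window for that visit.

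**The case against.** The strongest defence is that stopping at the end of scheduled visits is reasonable. It matches the stated objective, and it leaves the Kaplan-Meier curve before the limit unchanged. Past 5 years there is no scheduled contact. Deaths or re-interventions may still reach a site while event-free survivors are not seen, and anomaly-triggered visits sample selected patients. Lifting the limit everywhere could therefore bias the tail as well as make it imprecise. This stands, and it is why the remedy should not be to rerun every table without a limit.

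Three stronger readings are tempting, and the documents do not support them.

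- *A reader might infer that nothing in the authority's period is analysed.* The opinion asks for outcomes over the long term with results every year. Years 0 to 5 belong to that and are analysed; what is missing is the extension.
- *A reader might infer that a known body of late data is being thrown away.* No passage says that patients are followed to a common closing date. The absence of a maximum permits later follow-up but schedules none. Even under the common-closing assumption, almost no patient reaches year 6, so little late imaging would exist. The patient-years above show what is possible, not a measured loss.
- *A reader might infer that every curve is limited.* In SAP 2.4.3.2 it is unclear whether the limit covers aneurysm-related death and re-intervention, and the conversion rate during the procedure is not subject to it. Parts of the SAP are redacted, so later reporting elsewhere cannot be excluded.

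It is also fair that the protocol prints the opinion openly, and that a 5-year minimum is compatible with a longer horizon. Neither point reconciles Protocol 3.5 with Appendix 1.

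**Conclusion.** The point holds in a limited form. The protocol attributes to the authority a shorter horizon than the opinion it appends, with no agreement cited. The primary mortality curve, and at least the diameter, endoleak and migration curves, end at day 1826 although follow-up may continue, so no visible planned survival estimate under the limit reaches past 5 years.

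The amount of later follow-up is not stated. It is at most about 90 patient-years under uniform accrual and a common closing date, about 43 to 71 with assumed retention of 50% to 80%, and would contain little scheduled imaging.

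Separately, the limit can exclude imaging findings from a 5-year visit held on or after the anniversary. That would make the 5-year event-free proportions for these endpoints look too favourable. The size depends on visit timing and on how many findings are new at year 5, neither of which is given. The effect at the exact anniversary depends on the add-one-day rule applying to event times; for later visits it does not.

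**What to change.** 1. **Reconcile the horizon.** Align the Protocol Summary (introduction, objective, duration of participation), Protocol 2 and 3.5, and SAP 1.1 with Protocol 1.1.3 and Appendix 1, or cite the authority's agreement to 5 years.
2. **Keep the 5-year Kaplan-Meier estimate as the main result**, but replace the hard 1826-day limit with a defined 5-year visit window for analysis, so that findings from that visit count. State whether the add-one-day rule applies to event times.
3. **State which curves the limit covers**, in particular aneurysm-related death and re-intervention.
4. **Add a supplementary Kaplan-Meier analysis of all follow-up collected**, at least for all-cause mortality, aneurysm-related death and re-intervention, with numbers at risk after 5 years and censoring at last confirmed contact. Say whether data after 5 years are collected.

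The cost is a wording correction, a window rule and a few extra outputs, with no new patients or visits. The downside is that the tail will be imprecise and may reflect selective late reporting. It must be labelled descriptive and should not replace the 5-year estimate.
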